#### 9.4.1 Sn-117m-DTPA Activity

Gamma camera dosimetry will be used to evaluate whole-body distribution of Sn-117m-DTPA. Tin is an avid bone seeker, and its biodistribution is nearly identical to Tc-99m-MDP (Swailem *et al.*, 1998). The highest tin distribution is seen in bone surfaces (82%) with increased uptake in bone metastases. Focal and heterogenous bone uptake in Sn-117m-DTPA will be correlated with baseline Tc-99m-MDP. Other normal physiological tissue retention can be seen in liver, lungs, spleen, heart, and kidneys, and their uptake varies with the rates of clearance. The tumor uptake observed using the Sn-117m-DTPA scan must be  $\geq$  normal liver uptake observed on planar imaging.

#### Statistical Plan:

The Pearson's correlation coefficient method will be used to assess the correlation between the baseline technetium-99 bone scintigraphy measurement and the Sn-117m-DTPA uptake. If the observed data distribution is not appropriate to calculate the Pearson's correlation, *post hoc* analysis will be conducted using non-parametric methods or other methods suitable to the observed data distribution.

The gamma dosimetry scan measurements will be reported descriptively as the average and standard deviation of dosimetry scan measurements and plotted over time and grouped by organ systems.

#### 9.4.2 Overall Response Rate

A Fisher's exact 95% confidence interval will be calculated for the overall response rate. The denominator will include all patients who received at least one dose of study treatment and do not have major protocol deviations. Patients who do not have observed clinical response will be counted as negative responses.

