## 3.2 Exclusion Criteria

- 3.2.1 Patients must not have visceral metastases (such as liver and lung) as assessed by

abdominal/pelvic CT or chest X-ray within 12 weeks before starting study treatment.

- 3.2.2 Patients must not have malignant lymphadenopathy exceeding 3 cm in short-axis diameter.
- 3.2.3 Patients must not have imminent or established spinal cord compression based on clinical findings and/or MRI.
- 3.2.4 Patients who have had chemotherapy, immunotherapy, or external radiotherapy within 4 weeks prior to entering the study.
- 3.2.5 Patients must not have received systemic radiotherapy with radium-223, strontium-89, samarium-153, rhenium-186, or rhenium-188 for the treatment of bony metastases within 24 weeks before starting study treatment.
- 3.2.6 Patients who have not recovered from adverse events due to prior anti-cancer therapy (*i.e.*, have residual toxicities > Grade 1) with the exception of alopecia.
- 3.2.7 Patients must not have received any investigational agents within 4 weeks before starting study treatment, nor be scheduled to receive one during the planned treatment period.
- 3.2.8 Patients must not have unmanageable urinary incontinence.
- 3.2.9 Patients must not have had known non-pathological bone fractures within 2 months before starting study treatment.
- 3.2.10 Patients must not have a history of allergic reactions attributed to compounds of similar chemical or biologic composition to Sn-117m-DTPA.
- 3.2.11 Patients must not have uncontrolled intercurrent illness, including:
  - Any uncontrolled infection
  - Grade 2 or greater motor or sensory neuropathy
- 3.2.12 Patients with psychiatric illness/social situations that would limit compliance with study requirements.

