### 12.2.1 Definitions

Evaluable for Toxicity. All patients will be evaluable for toxicity from the time of their first treatment with Sn-117m-DTPA.

Evaluable for Objective Response. Only those patients who have measurable disease present at baseline, have received at least one cycle of therapy, and have had their disease re-evaluated will be considered evaluable for response. These patients will have their response classified according to the definitions stated below. (Note: Patients who exhibit objective disease progression prior to the end of cycle 1 will also be considered evaluable.)

Evaluable Non-Target Disease Response. Patients who have lesions present at baseline that are evaluable but do not meet the definitions of measurable disease, have received at least one cycle of therapy, and have had their disease re-evaluated will be considered evaluable for non-target disease. The response assessment is based on the presence, absence, or unequivocal progression of the lesions.

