### 12.2.2 Disease Parameters

Measurable Disease. Measurable lesions are defined as those that can be accurately measured in at least one dimension (longest diameter to be recorded) as  $\geq 20$  mm ( $\geq 2$  cm) by chest x-ray or as  $\geq 10$  mm ( $\geq 1$  cm) with CT scan, MRI, or calipers by clinical exam. All tumor measurements must be recorded in millimeters (or decimal fractions of centimeters).

Note: Tumor lesions that are situated in a previously irradiated area might or might not be considered measurable.

**Malignant Lymph Nodes.** To be considered pathologically enlarged and measurable, a lymph node must be  $\geq 15$  mm ( $\geq 1.5$  cm) in short axis when assessed by CT scan (CT scan slice thickness recommended to be no greater than 5 mm [0.5 cm]). At baseline and in follow-up, only the short axis will be measured and followed.

**Non-Measurable Disease.** All other lesions (or sites of disease), including small lesions (longest diameter  $< 10$  mm [ $< 1$  cm] or pathological lymph nodes with  $\geq 10$  to  $< 15$  mm [ $\geq 1$  to  $< 1.5$  cm] short axis), are considered non-measurable disease. Bone lesions, leptomeningeal disease, ascites, pleural/pericardial effusions, lymphangitis cutis/pulmonitis, inflammatory breast disease, and abdominal masses (not followed by CT or MRI), are considered as non-measurable.

Note: Cystic lesions that meet the criteria for radiographically defined simple cysts should not be considered as malignant lesions (neither measurable nor non-measurable) since they are, by definition, simple cysts.

‘Cystic lesions’ thought to represent cystic metastases can be considered as measurable lesions, if they meet the definition of measurability described above. However, if non-cystic lesions are present in the same patient, these are preferred for selection as target lesions.

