**For Patients with Non-Measurable Disease (i.e., Non-Target Disease)**

Non-Target Lesions	New Lesions	Overall Response
CR	No	CR
Non-CR/non-PD	No	Non-CR/non-PD*
Not all evaluated	No	not evaluated
Unequivocal PD	Yes or No	PD
Any	Yes	PD

\* ‘Non-CR/non-PD’ is preferred over ‘stable disease’ for non-target disease since SD is increasingly used as an endpoint for assessment of efficacy in some trials so to assign this category when no lesions can be measured is not advised

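### Section 9.4.2 does not define its overall response and includes patients who cannot have a partial response, so the rate depends on the unstated share with measurable disease

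*Combined protocol and SAP*

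**What the plan says.** Section 9.4.2 has three elements. The interval: "A Fisher's exact 95% confidence interval will be calculated for the overall response rate". The denominator: "The denominator will include all patients who received at least one dose of study treatment and do not have major protocol deviations". The handling of everyone else: "Patients who do not have observed clinical response will be counted as negative responses". It gives no definition of clinical response and names no response criteria. Its denominator agrees with the Per Protocol Population that Section 9.6.2 assigns to efficacy analyses.

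Section 12.2.1 describes whose objective response can be assessed: "Only those patients who have measurable disease present at baseline, have received at least one cycle of therapy, and have had their disease re-evaluated". It also has a second category, for non-target response, which covers "Patients who have lesions present at baseline that are evaluable but do not meet the definitions of measurable disease".

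Section 12.2.2 opens its list of non-measurable disease with "Bone lesions, leptomeningeal disease, ascites, pleural/pericardial effusions". On nodes, Section 3.2 says: "Patients must not have malignant lymphadenopathy exceeding 3 cm in short-axis diameter". Section 3.2 also excludes visceral metastases, and Section 3.1.3 requires two or more skeletal metastases. No eligibility criterion requires measurable disease.

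**The concern.** A response rate can be interpreted only if the reader knows what counts as a response and if the patients in the denominator could have shown one. Section 9.4.2 fails the first condition and, on its most natural reading, largely fails the second. The population is selected for bone disease, with visceral disease excluded and node size capped. Patients with bone disease only are eligible by design, and a partial response is closed to them. Counting them as negative makes the estimate a mixture of the drug's effect on soft tissue and the baseline case mix. Two trials with the same drug effect but different proportions of measurable nodes would report different rates. The exact interval on the larger denominator would also look narrower than the information about soft-tissue response justifies.

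**Working it through.** The plan gives no target, threshold or sample-size calculation for the overall response rate, so there is no stated figure to reproduce. The check has two parts.

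**Which response does Section 9.4.2 mean?** Sections 9.4.1 to 9.4.9 follow objectives 1.2.2 to 1.2.9 in order:

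- 9.4.1, dosimetry: 1.2.2
- 9.4.2, overall response: 1.2.3
- 9.4.3, skeletal events: 1.2.4
- 9.4.4 and 9.4.5, pain response and its duration: 1.2.5 and 1.2.6
- 9.4.6, PSA and ALP: 1.2.7
- 9.4.7, patient-reported outcomes: 1.2.8
- 9.4.8 and 9.4.9, PFS and OS: 1.2.9

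So 9.4.2 is the tumour-response analysis for objective 1.2.3. Pain and PSA response have sections of their own.

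**Which routes to a tumour response exist for a bone-only patient?**

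- Partial response in target lesions (12.2.4.1): none, because bone lesions are non-measurable (12.2.2).
- Partial response in the table for non-measurable disease (12.2.4.3): not offered. The outcomes are CR, non-CR/non-PD, PD and not evaluated.
- PCWG3 bone criteria (12.1.1): the part adopted concerns progression. Change is recorded as new or no new lesions, and a change in uptake intensity alone is not regression.
- Non-target CR (12.2.4.2): open, but it needs all non-target lesions to disappear and the tumour marker level to be normal.

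Measurable disease in this trial is mainly nodal: at least 1.5 cm in short axis to be measurable (12.2.2), and at most 3 cm to be eligible (3.2.2).

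**Size.** Inputs: N = 25 (Section 9.2), taken as all treated with no major deviations (assumption); m = patients with measurable baseline disease (not in the documents, shown as a range); r = response rate among those m (assumption). If no non-target CR occurs in the others:

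reported rate = (m × r) / 25 = r × (m/25), with a ceiling of m/25.

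| m | ceiling m/25 | reported rate if r = 20% | if r = 30% | if r = 50% |
|---|---|---|---|---|
| 5 | 20% | 4.0% | 6.0% | 10.0% |
| 10 | 40% | 8.0% | 12.0% | 20.0% |
| 13 | 52% | 10.4% | 15.6% | 26.0% |
| 20 | 80% | 16.0% | 24.0% | 40.0% |
| 25 | 100% | 20.0% | 30.0% | 50.0% |

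**Intervals**, taking the exact interval as Clopper-Pearson:

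- m = 10, 3 responders: 3/10 = 30.0% (6.7 to 65.2); 3/25 = 12.0% (2.5 to 31.2).
- m = 5, 2 responders: 2/5 = 40.0% (5.3 to 85.3); 2/25 = 8.0% (1.0 to 26.0).

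In the first example the interval narrows from about 59 to about 29 percentage points, although the number of patients who could show a partial response is unchanged.

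**The case against.** Four arguments can be made for the plan.

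First, Section 12.2.1 defines evaluability under a heading about soft-tissue progression; it does not set an analysis denominator. The analysis set comes from Section 9.6.2, and 9.4.2 agrees with it. This stands: the two sections do not state rival denominators. The mismatch remains, because the analysis set includes patients whom 12.2.1 does not regard as evaluable for objective response, and the plan does not say how the two fit together.

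Second, Section 9.4.2 never says RECIST. Section 9.6.2 points to PCWG3 for bone, the adopted PCWG3 parts include PSA response, and Section 9.1 uses the abbreviation ORR for the primary pain endpoint, with anyone given any study drug in the denominator. On a pain or PSA reading every patient could respond and there would be no dilution. The order of the sections makes those readings unlikely, but the text does not rule them out. That is itself the case for a definition.

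Third, counting patients without an observed response as negative is a normal conservative rule. That holds for patients who could have responded and were not seen to. It does not extend to patients for whom partial response is not an available category.

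Fourth, the rate is secondary and descriptive, and Section 9.4.8 already plans clinical PFS including PCWG3 bone progression. This limits the consequence. However, clinical PFS also counts increasing pain as progression, so it does not isolate the PCWG3 result.

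A reader might go further and infer that bone-only patients are automatically non-responders. The documents do not support that: the non-target category in 12.2.1 and its CR route are open to them, however demanding.

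**Conclusion.** The point holds as a defect of definition and denominator in a secondary endpoint. Section 9.4.2 leaves its response undefined. On the reading that fits the structure of the plan, it includes patients who cannot have a partial response and whose only route is non-target CR. If no such CR occurs, the reported rate equals the response rate in measurable disease multiplied by m/25: with an assumed 30% response rate, 6.0% at m = 5, 12.0% at m = 10 and 24.0% at m = 20. These figures rest on assumed values of m and r, on 25 patients in the denominator, and on a tumour-response reading of 9.4.2.

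Three stronger statements might be inferred and should not be made. That most enrolled patients lack measurable disease is not shown, since nodes of 1.5 to 3 cm are both eligible and measurable and no share is given. That the rate is driven towards zero does not follow: it is scaled by an unknown proportion and is small only if that proportion or the response rate is small. That the denominator is every treated patient is inaccurate, because those with major protocol deviations are left out.

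No test or threshold is attached to this rate, and the decision rule on sustained pain response does not use it.

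**What to change.** Amend Section 9.4.2 as follows.

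- Define the response as RECIST 1.1 objective response (CR or PR).
- Report it with its exact 95% interval in patients with measurable disease at baseline, and state n. Restrict on the baseline characteristic only: a treated patient with measurable disease and no follow-up scan stays in as a non-responder, as 9.4.2 already intends.
- For the whole efficacy population, report the 24-week PCWG3 progression-free proportion as the analysis of objective 1.2.3. The Study Calendar already schedules imaging at 24 weeks. Report any non-target CR separately.
- Keep PSA response (9.4.6) and pain response (9.4.4) as separate endpoints, and reserve the abbreviation ORR for one of its two present uses.

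This changes wording only and adds no patients or visits. The cost is a smaller denominator and a wider interval for the response rate; at m = 10 with 3 responders it would run from 6.7% to 65.2%. That width reflects how little the trial can say about soft-tissue response.

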#### 9.4.3 Time to First Symptomatic Skeletal Event

The time from study enrollment to 1) the first use of external-beam radiation therapy to relieve skeletal symptoms, 2) new symptomatic pathologic vertebral or non-vertebral bone fractures, 3) spinal cord compression, or 4) tumor-related orthopedic surgical intervention will be evaluated.

#### 9.4.4 Overall Pain Response Rate

The rate of achievement of pain index  $\leq 3$  within 12 weeks from the first Sn-117m-DTPA will be evaluated.

#### 9.4.5 Duration of Pain Response

The time from the achievement of pain response (pain index  $\leq 3$ ) to the recurrence of pain (pain index  $\geq 4$ ) will be evaluated.

#### 9.4.6 Serum Prostate-Specific Antigen and Alkaline Phosphatase Responses

Levels of serum PSA and ALP will be measured at 4-week intervals and used to determine response rates for each molecular marker.

PSA response rates will be determined for the following benchmarks:

- $\geq 30\%$  reduction of the blood level, compared to the baseline value
- $\geq 50\%$  reduction of the blood level, compared to the baseline value
- Confirmed PSA response:  $\geq 50\%$  reduction of the blood level, compared to the baseline value, and confirmed by a second PSA value approximately 4 or more weeks later

ALP response rates will be determined for the following benchmarks:

- $\geq 50\%$  reduction of the blood level, compared to the baseline value
- Confirmed ALP response:  $\geq 50\%$  reduction of the blood level, compared to the baseline value, and confirmed by a second ALP value approximately 4 or more weeks later

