## 6.3 General Concomitant Medication and Supportive Care Guidelines

### 6.3.1 Concomitant Prostate Cancer Therapy

- Patients receiving bisphosphonates or denosumab prior to enrollment can maintain therapy throughout all or part of the study. The bisphosphonate may be stopped or

started at the discretion of the investigator throughout the study (*i.e.*, both treatment phase and follow-up). Injection of bisphosphonates should be done at least 2 hours before or after study drug administration.

- Patients who have not undergone bilateral orchiectomy are allowed and should receive LHRH agonists or antiandrogen such as bicalutamide throughout the study (*i.e.*, both treatment phase and follow-up).
- Cytotoxic chemotherapy, androgen receptor blockers, androgen biosynthesis inhibitors, other systemic radioisotopes, hemi-body external radiotherapy, and other investigational drugs should not be used during the treatment period. These treatments can be given if at least 8 weeks after the last injection.
- Colony stimulating factors (*e.g.*, erythropoietin and granulocyte colony stimulating factors) and transfusions products (*e.g.*, red blood cell transfusion, and/or platelet transfusion) as dictated by standard practice are acceptable while the subject is enrolled in the study.

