## 6.5 Duration of Follow-Up

Patients will be followed every 2 weeks during treatment (16 weeks), then every 4 weeks until Week 28, and then every 3 months or as clinically indicated for 12 months after the first Sn-117m-DTPA dose or until death, whichever occurs first. After the 1-year follow-up period, dates of death will be collected for all patients until the final patient completes his 1-year follow-up. Patients removed from study for unacceptable adverse event(s) will be followed until resolution or stabilization of the adverse event.

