## 7. DOSING DELAYS/DOSE MODIFICATIONS

No Sn-117m-DTPA dose modification is allowed. Patients will be monitored continuously for AEs throughout the study. Patients must be instructed to notify their physician immediately for any and all side effects. Treatment interval is scheduled every 8 weeks or every 56 days with a window period of +/- 7 days for all time points. If the treatment needs to be delayed due to an adverse event, study drug administration can be delayed up to 8 weeks for recovery, with the following conditions:

- Hematological toxicities must resolve to CTCAE grade 1 or less (or, if abnormal at baseline, not more than one grade above baseline) prior to administration of the next Sn-117m-DTPA dose. In the absence of recovery after 4 weeks, patients are to discontinue further study drug administrations.
- Non-hematological toxicities must resolve to CTCAE grade 2 (gastrointestinal events) or grade 3 (other toxicities) prior to administration of the next dose.
- If patients experience spinal cord compression during the treatment phase, Sn-117m-DTPA administration can continue with up to a 4-week delay if the patient is adequately treated with steroids, local SBRT, or surgery.
- If patients experience traumatic fracture in weight-bearing bones during the treatment phase, the study drug administration should be delayed 4 weeks from the fracture.

As a general approach, it is suggested that all AEs be managed with supportive care when possible at the earliest signs of toxicity.

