### 9. STATISTICAL CONSIDERATIONS

#### 9.1 Study Design/Endpoints

This is a single-arm, open-label phase 2 study to evaluate the efficacy of Sn-117m-DTPA on

sustained pain response in patients with CRPC metastatic to at least two bone sites, with at least one clinically meaningful pain at baseline ( $\geq 4$  on an 11-point pain intensity scale). Sustained pain-response is defined as: 1) achieving pain index  $\leq 3$  within a 12-week period and 2) maintaining that pain index  $\leq 3$  over a 16-week time period (beginning when the pain index  $\leq 3$  is initially achieved). The maximum duration of follow-up required to declare a patient a responder is 28 weeks, representing a patient who initially achieves pain index  $\leq 3$  toward the end of the 12-week period and is followed for an additional 16 weeks to confirm maintenance of pain index  $\leq 3$ .

Eligible patients will be assigned to receive Sn-117m-DTPA at 20 mCi/70 kg (0.28 mCi/kg) every 8 weeks for two cycles. Treatment will last for 16 weeks with two treatment injections given at 8-week intervals. The study utilizes a mini-max Simon two-stage design to assess anti-tumor activity and pain benefit of Sn-117m-DTPA.

Patients are not allowed to receive external radiation within 12 weeks from the start of treatment administration. If their pain index does not reach  $\leq 3$  after 12 weeks, they are not meeting the primary endpoint, and they can then get external radiation for pain control.

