## 9.4 Analysis of Secondary Endpoints

Secondary endpoints will be summarized depending on data type. Categorical endpoints will be summarized by frequency and percent. Continuous variables will be summarized by mean and standard deviation at each assessment time point. Time-to-event endpoints will be summarized by Kaplan-Meier Methods. Safety and toxicity will be assessed through the frequency and percent of adverse events (AEs), serious adverse events (SAEs), and adverse events of special interests (AESIs). Toxicity will be assessed using Common Terminology Criteria for Adverse

Events v 5.0 (CTCAE). Safety and toxicity will also be assessed by patient-reported outcomes and adverse events (PRO-CTCAE) captured by digital instruments during treatment and 8 weeks after the last injection to monitor for acute toxicity and every 2-4 weeks for 6 months post-therapy for monitoring of long-term toxicity. CTCAE grades for the corresponding time period will be presented in conjunction with PRO-CTCAE scores. PSA and ALP response rates will be calculated for each of the above defined categories with the corresponding confidence intervals. *Post-hoc* analysis on PSA and ALP levels may be conducted to explore possible trends in PSA and ALP levels. Time to the first symptomatic skeletal event will be analyzed using the Kaplan-Meier method. Estimation and confidence intervals for the median time to first symptomatic skeletal event will be provided. Patients who did not have a symptomatic skeletal event will be censored at the last study visit. PFS will be analyzed in a similar manner as the time to first skeletal event. Patients who did not have observed clinical progression will be censored at the last assessment.

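### PSA and ALP response have no stated window and no cut at new anticancer therapy, so a fall after a permitted switch can be scored as a response to Sn-117m-DTPA

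*Combined protocol and SAP*

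**What the plan says.** Section 9.4.6 sets the measurement rule: "Levels of serum PSA and ALP will be measured at 4-week intervals and used to determine response rates for each molecular marker". Each benchmark is a "reduction of the blood level, compared to the baseline value", at 30% and 50% for PSA and 50% for ALP. The confirmed PSA version must be "confirmed by a second PSA value approximately 4 or more weeks later", and the ALP version is built the same way. Section 9.4 adds only that "PSA and ALP response rates will be calculated for each of the above defined categories with the corresponding confidence intervals".

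On timing, section 9.1 states: "Treatment will last for 16 weeks with two treatment injections given at 8-week intervals". Section 7 adds that, for an adverse event, "study drug administration can be delayed up to 8 weeks for recovery". Section 6.3.1 bars chemotherapy, androgen receptor blockers, androgen biosynthesis inhibitors and other systemic radioisotopes during the treatment period, then says: "These treatments can be given if at least 8 weeks after the last injection".

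Section 6.5 schedules visits every 4 weeks from the end of treatment to Week 28, "then every 3 months or as clinically indicated for 12 months after the first Sn-117m-DTPA dose or until death". Study calendar footnote a instead ends follow-up visits at one year or at progression. Serum chemistry, which includes ALP (footnote b), and PSA are both marked for the post-treatment and follow-up visits.

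**The concern.** In a single-arm trial, a PSA or ALP response rate is read as the activity of the study drug. That reading fails if the eligible values include those taken on a different PSA-lowering drug. Patients enter with a rising PSA after earlier therapy (sections 3.1.1 and 3.1.2), so moving to another drug during follow-up is plausible, and the plan allows it. There is no control arm in which the same contamination would show. With no window fixed in advance, the analyst would also have to choose one after seeing the data.

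**Working it through.** The plan states no target rate or power for PSA or ALP response, so there is no figure to reproduce. The check covers timing, the scoring rule, direction and scale.

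**1. When new therapy is allowed.** Earliest week = week of last injection + 8. The measurements are taken at Weeks 4, 8, 12, 16, 20, 24 and 28 (7 values), assuming they stay on those weeks if an injection is delayed.

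| Case | Last injection | Therapy allowed from | Values after that, to Week 28 |
|---|---|---|---|
| One injection only | Week 0 | 0 + 8 = Week 8 | 12, 16, 20, 24, 28 (5 of 7) |
| Two, on time | Week 8 | 8 + 8 = Week 16 | 20, 24, 28 (3 of 7) |
| Second delayed 8 weeks | Week 16 | 16 + 8 = Week 24 | 28 (1 of 7) |

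If the 3-monthly visits at about Weeks 40 and 52 also count, the figures become 7, 5 and 3 of 9.

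**2. Whether a confirmed response fits.** With two on-time injections, a first qualifying value at Week 20 and a second at Week 24 are 4 weeks apart. Both fall after therapy became allowed, so the confirmation rule does not screen out the next drug.

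**3. What a post-switch fall must achieve.** The reference is study baseline, not the value at the switch. Let k be PSA at the switch divided by baseline PSA. The fall needed from the switch value is 1 − 0.5/k for the 50% benchmark and 1 − 0.7/k for the 30% benchmark.

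- k = 1: 50% and 30%
- k = 1.5: 67% and 53%
- k = 2: 75% and 65%

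The contamination is therefore real but harder to reach when PSA has risen on study.

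**4. Direction.** A response is a threshold met at any eligible time. Adding later values can turn a non-responder into a responder and never the reverse.

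**5. Scale.** One misattributed responder among 25 patients moves the rate by 1/25 = 4 points. More generally, the rate as scored is r + (1 − r) × f × q. Here r is the rate before any switch, f is the share of patients who switch while values are still collected, and q is the share of switchers (not already responders) whose later fall meets the benchmark relative to study baseline. The documents give none of these. As pure assumptions, take r = 10%, f = 30% to 60% and q = 0% to 40%:

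- q = 0: 0.10 + 0.90 × f × 0 = 10.0%, so no bias.
- f = 30%, q = 20%: 0.10 + 0.90 × 0.30 × 0.20 = 15.4%, or 1.4 extra responders in 25 (25 × 0.054 = 1.35).
- f = 60%, q = 40%: 0.10 + 0.90 × 0.60 × 0.40 = 31.6%, or 5.4 extra responders in 25.

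The width of this range is the finding. The formula shows the mechanism and does not estimate the bias.

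**6. Whether another section closes the gap.**

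- Section 12.1.1 tells the reader to disregard PSA rises before 12 weeks, which sets no closing date.
- Section 9.6.2 removes major protocol violations, and permitted therapy is not one.
- Objective 1.2.3 names 24 weeks for PCWG3 efficacy, but 9.4.6 does not adopt it, and Weeks 20 and 24 would still follow Week 16.
- Overall pain response, by contrast, has an explicit 12-week limit in 9.4.4.

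**The case against.** The strongest reply is that the plan implies a window. Values every 4 weeks run only to Week 28, so that series is the natural reading of 9.4.6. Footnote a would also take patients who switch at progression out of scheduled follow-up, and 1.2.3 together with 12.1.1 offers 24 weeks as a candidate timepoint for PSA. The endpoint is descriptive, with no hypothesis or threshold attached.

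Much of this stands. It narrows the exposure, and a reader should not assume that everyone who switches within 12 months is affected. It does not close the gap. On the 24-week reading, two scheduled values remain open after Week 16; on the Week 28 reading, three do. Footnote a conflicts with 6.5, and it governs visits rather than scoring. Under 9.4.8 a PSA rise alone is not clinical progression, so a patient switched for that reason could remain in follow-up.

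Two stronger readings are tempting and are not supported. A reader might infer that any patient whose PSA halves on the next drug becomes a confirmed responder. The reference is study baseline: at 1.5 times baseline, halving gives 0.75 times baseline, a 25% fall that misses even the 30% benchmark, and at twice baseline it gives no fall at all. A reader might also attach a definite number of points to the bias, but published-style response rates measured from the start of the next drug cannot stand in for falls from study baseline. The documents supply neither those rates nor the share who switch.

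**Conclusion.** The point holds in this limited form. Section 9.4.6 has neither a response window nor a cut at new anticancer therapy, and 6.3.1 permits that therapy while PSA and ALP are still being measured. Followed literally, the plan can credit Sn-117m-DTPA with falls produced by the next treatment, and the error runs upward only. This rests on the scoring rule and the schedule, not on any assumed uptake. The size is unknown: it depends on how many patients switch and on how far their PSA or ALP has moved from baseline by then. A reader might infer that collection is unlimited, but it ends at about 12 months at the latest; what is missing is a limit in the response definition. The correction should be made before analysis, but the primary pain endpoint and its two-stage decision rule do not depend on it.

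**What to change.** In 9.4.6, score only PSA and ALP values, confirming value included, obtained before the start of any new systemic anticancer therapy or radioisotope. State the outer limit of the window: for example Week 24 to match objective 1.2.3, or Week 28 to match the 4-weekly visits. List later values, or use them only in a sensitivity analysis that ignores new therapy. Section 6.1 allows retreatment, which can fall outside either window, so report responses during it separately. Reconcile 6.5 with calendar footnote a on whether progression ends follow-up visits.

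Confirm that the case report form records start dates of new anticancer therapy through follow-up. Section 6.3.3 requires concurrent drugs to be captured but does not expressly cover start dates or therapy after study treatment.

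The cost is a few sentences of text and possibly one data field. The permitted therapies do not change. The downside is that the reported rates may be slightly lower, because late responses outside the window are not scored.
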